7.5.3 Missing Data

It is anticipated that there will be no missing data expected for the primary implementation outcome since this entails data abstraction from the EHR after the index ED visit. One scenario in which missing data may arise is if the participant withdraws consent prior to medical record abstraction. To minimize missing data for the primary effectiveness outcome, the initial assessment conducted at the follow-up visit will be the ETP, which can be done over the phone to maximize availability. Per Section 12.10 of the protocol, any missing primary outcome data will be considered as failures (i.e., no provision of ED-initiated BUP, not engaged in formal addiction treatment for OUD on Study Day 30).

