12.10 Missing Data

Patients lost to follow-up will not be counted as successes for either primary outcome, and, because counted as failures, will not generate missing data. Accordingly, we ignore the possibility

of loss to follow-up in the power calculations, and will assume that losses are failures for the purposes of the actual data analysis.

Several strategies will be implemented to minimize the likelihood and the rate of potential missing data in the proposed study. Timely data entry combined with frequent, planned, and scheduled evaluation of data completeness reports will trigger protocols for tracking and obtaining missing data. In our previous research, we developed patient tracking and communication protocols that resulted in very low rates of missing data. These field tested procedures with proven effectiveness, with the necessary site specific adjustments, will be disseminated across all study sites.

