The primary effectiveness outcome measure is binary variable reflecting engagement in addiction treatment on the 30th day post-index ED visit. The outcome will be based on patient participant self-report on the Engagement in Treatment: Participant (ETP) form and confirmed by facility and/or treating clinician on the Engagement in Treatment: Facility (ETF) form. If a patient participant reports being in treatment (i.e., ETMEDTRT="1") but there is no confirmation from a facility or clinician (i.e., no ETFs are completed, or all ETENGAGE="0") then the individual is considered not engaged in formal addiction treatment for OUD. Similarly, if there is an ETF indicating the individual was engaged in treatment (i.e., ETENGAGE="1") but this is not in line with self-report (i.e., ETMEDTRT="0", or the facility name does not match the self-reported facility) then the patient participant is considered not engaged in formal addiction treatment for OUD. If there is no ETP completed or if an ETF is completed but the facility did not complete confirmation the individual was engaged in treatment (i.e., ETENGAGE is missing on an existing ETF), then the primary effectiveness outcome is considered missing. If the patient participant self-reports not being in treatment then they are considered not engaged in formal addiction treatment for OUD, regardless of any ETF forms completed. Lastly, if the ETP is not completed but there is an ETF completed, the primary effectiveness outcome measure is considered missing.

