7.5.4 Secondary Analyses Related to the Primary Effectiveness Outcome

A secondary analysis akin to the primary effectiveness outcome will also be implemented that addressed potential surveillance bias. Sites continued to attempt contact with patient participants who did not attend the follow-up visit within the targeted window (44 days, inclusive). Due to the stepped wedge this may result in a bias in that patient participants enrolled earlier have more of a chance of obtaining the primary effectiveness outcome. An analysis will be performed for treatment engagement that requires the self-report to have been obtained within the 44-day target window. Other than this requirement the operational definition follows Section 7.3.

An additional secondary analysis of the treatment engagement outcome measure will be implemented to assess whether there are differences in the rate of engagement at Day 30 between those who received ED-initiated BUP and those who did not.

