	Hispanic or Latino (N=)	Not Hispanic or Latino (N=)	Hispanic or Latino (N=)	Not Hispanic or Latino (N=)
Self-report Treatment Engagement	N	N		
Facility confirmed Treatment Engagement	N	N		
Missing primary effectiveness outcome (i.e., to be imputed as non-engaged)	N	N		
Engagement in formal addiction treatment for OUD at Day 30	N (XX.x%)	N (XX.x%)		

**Table 28: Final Covariate Adjusted Model Analysis Results
for Primary Effectiveness Outcome**

Covariate ¹	N	Coefficient	95% Credible Interval
Study Phase			
BEP	N	[ref]	[ref]
IFEP	N	X.x	X.xx; X.xx
Sex			
Male	N	[ref]	[ref]
Female	N	X.x	X.xx; X.xx
Race			
White	N	[ref]	[ref]
Black	N	X.x	X.xx; X.xx
Other	N	X.x	X.xx; X.xx
Ethnicity			
Not Hispanic/Latino		[ref]	[ref]
Hispanic/Latino		X.x	X.xx; X.xx
Sex-by-study phase interaction ²			
Male	N	X.x	X.xx; X.xx
Female	N	X.x	X.xx; X.xx
Race-by-study phase interaction ²			
White	N	X.x	X.xx; X.xx
Black	N	X.x	X.xx; X.xx
Other	N	X.x	X.xx; X.xx
Ethnicity-by-study phase interaction ²			
Not Hispanic/Latino	N	X.x	X.xx; X.xx
Hispanic/Latino	N	X.x	X.xx; X.xx

¹ Note that only covariates which remained in the final covariate-adjusted model will be included in this table.

² Coefficient and corresponding credible intervals are presented for the intervention effect in a particular subgroup (e.g., males).

Table 29: COVID-19 Sensitivity Analyses Results for Primary Effectiveness Outcome

Sensitivity Analysis	GLMM		Bayesian Analysis		
	Intervention Coefficient	p-value	Risk Difference Estimation Time Point	Risk Difference	95% Credible Interval
Pre-COVID data	X.xx	x.XXX	Mid-point (day 632)	X.xx	X.xx; X.xx
			COVID-19 Pause (day 1423)	X.xx	X.xx; X.xx
COVID pause removed	X.xx	x.XXX	Mid-point (day 632)	X.xx	X.xx; X.xx
			COVID-19 Pause (day 1423)	X.xx	X.xx; X.xx

Table 30: Summary of Treatment Engagement at Day 30 during the IF Evaluation Period by ED-initiated BUP Status: All Patient-participants (Missing Engagement Status Imputed as Not Engaged)

ED-initiated BUP Status	Pre-IF Cohort (N =)	Post-IF Cohort (N =)
No	N (XX.x%)	N (XX.x%)
Yes	N (XX.x%)	N (XX.x%)

Table 31: Summary of Treatment Engagement at Day 30 during the IF Evaluation Period by ED-initiated BUP Status: Patient-participants with Non-missing Engagement Status (No Imputation)

ED-initiated BUP Status	Pre-IF Cohort (N =)	Post-IF Cohort (N =)
No	N (XX.x%)	N (XX.x%)
Yes	N (XX.x%)	N (XX.x%)

Table 32: Analysis of Treatment Engagement at Day 30 during the IF Evaluation Period by ED-initiated BUP Status

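### Scoring missing Day-30 engagement as failure is never varied in any inferential analysis of the IF-versus-baseline effectiveness comparison

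*SAP*

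**What the plan says.** Protocol 12.10 states "Patients lost to follow-up will not be counted as successes for either primary outcome" and adds that such patients, "because counted as failures, will not generate missing data". The next sentence begins "Accordingly, we ignore the possibility", referring to loss to follow-up in the power calculations. No expected loss rate is given. SAP 7.5.3 carries the rule forward: "any missing primary outcome data will be considered as failures".

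SAP 7.3 defines when the outcome is missing. A success needs a patient report (ETP form) and a matching facility confirmation (ETF form). It ends with this case: "if the ETP is not completed but there is an ETF completed, the primary effectiveness outcome measure is considered missing". Under 7.5.3 that patient becomes a failure.

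SAP 7.5.4 notes that sites kept trying to reach patients after the visit window. As a possible consequence, it says that "patient participants enrolled earlier have more of a chance of obtaining the primary effectiveness outcome". It therefore adds an analysis that "requires the self-report to have been obtained within the 44-day target window" and otherwise keeps the definition in 7.3.

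SAP 7.5.2 lists two sensitivity analyses, both about the COVID-19 enrolment pause. In SAP 16.1.4, Tables 22 and 23 count missing outcomes by period and by site and period, and Table 24 holds the period effect. Tables 30 to 32 compare engagement by buprenorphine status with and without imputation. The Revised SAP section at the end of the SAP replaces the planned model with logistic regression on site and evaluation period, without time.

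**The concern.** Scoring the lost as failures leaves the period contrast unbiased if none of them was engaged. Otherwise the contrast absorbs any difference in loss between periods, and the interval treats the assigned values as observed. SAP 7.3 is itself a reason not to take the favourable case for granted: it provides for a patient with a completed facility form who is nonetheless missing, and so a failure, because the patient form was not obtained. Protocol 8.2 and 12.1 assess engagement by direct contact with the facility or clinician.

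Baseline precedes IF at every site. By the dates in SAP 3.3.6, the two periods overlap across sites for only 85 days (9 October 2018 to 1 January 2019, inclusive). A drift in ascertainment over calendar time is therefore nearly a difference between periods, and the final model has no time term to absorb it. What is at stake is whether an effectiveness result, null or positive, can be told apart from a difference in retention.

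**Working it through.** **1. The plan's own power figure.** Protocol 12.9.1 claims power above 0.8 for the optimistic effectiveness scenario (25% versus 50%) at ICC below 0.3, and lower power for less separated scenarios. Losses are ignored. A simulation with 4 sites of 120 + 120 patients, 3-month offsets, arm, month and site terms, and one-sided 0.05 gave 0.90 at ICC 0 and 0.88 to 0.94 for ICC 0.05 to 0.3. For 25% versus 40% it gave 0.54 to 0.61. Site fixed effects and a logistic random-intercept generator stood in for GLIMMIX and the Parzen method. The claim is reproduced.

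**2. Which planned analysis varies the rule for the period effect?**

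| Analysis | What it changes | Varies missing = failure for IF versus baseline? |
|---|---|---|
| COVID-19 re-cuts (7.5.2) | dates and time scale | no |
| 44-day analysis (7.5.4) | contact window | no; it sets no other missing-data rule and does not say how late reports are coded |
| Tables 5, 7, 22, 23 | counts, reasons and attendance | descriptive only |
| Table 31 | non-missing rates by buprenorphine status; the shell has pre-IF and post-IF columns | descriptive only |
| Table 32 | complete-case test | tests buprenorphine status, not period |
| Table 24 | period effect | no alternative handling |

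**3. Bias formula.** Let L0 and L1 be the loss in the baseline and IF periods, and e the engagement among the lost, taken as equal in both. The recorded rate is the true rate minus L × e, so the bias in IF minus baseline is e × (L0 − L1).

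| e (assumed) | 5-point difference in loss | 10-point difference |
|---|---|---|
| 0.40 | 0.40 × 5 = 2.0 points | 4.0 |
| 0.25 (planned baseline rate, Protocol 12.5) | 0.25 × 5 = 1.25 | 2.5 |
| 0.20 (half of 0.40) | 0.20 × 5 = 1.0 | 2.0 |
| 0 | 0 | 0 |

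**4. Effect on the test with no true effect.** Assumptions: 480 per period, 40% engagement in both, loss independent of engagement, final site-plus-period model, 3,000 replicates, nominal one-sided 0.05.

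| Follow-up baseline / IF | Shift | Rejects favouring IF | Rejects the other way |
|---|---|---|---|
| 80% / 80% | 0 | 5% | 5% |
| 80% / 75% | −2.0 points | 0.9% | 17% |
| 80% / 70% | −4.0 | 0.1% | 37% |
| 75% / 80% | +2.0 | 18% | 1.1% |
| 70% / 80% | +4.0 | 39% | 0.1% |

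Under the same independence assumption, a complete-case comparison would be centred on zero in every row.

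**5. Effect on a true 25% versus 40%.** The recorded difference is 0.40 × IF follow-up − 0.25 × baseline follow-up.

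- No loss: 0.40 − 0.25 = 15 points.
- 80% / 80%: 0.32 − 0.20 = 12 points.
- 80% / 75%: 0.30 − 0.20 = 10 points.
- 80% / 70%: 0.28 − 0.20 = 8 points.

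In the time-adjusted model at ICC 0, power falls from 0.53 to 0.46, 0.35 and 0.28. A plain two-proportion test, which like the final model has no time term but also ignores site, keeps power of 0.90 at 80% / 70%. Without time in the model, the main damage is to the size of the estimate.

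**6. Direction.** SAP 7.5.4 raises an advantage for earlier enrollees, who are mainly baseline patients. That corresponds to rows 2 and 3 of the table in step 4.

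**The case against.** A reader might infer that the plan has no check at all on unequal follow-up. It does. The 44-day analysis was written for the enrolment-date mechanism, and Tables 7, 22 and 23 show attendance and missingness by period. Crude complete-case rates could even be worked out from Table 22. This stands. However, those tables carry no adjusted estimate or interval, and equalising the window does not test differential loss inside it. The 44-day analysis also has no entry in the table list in SAP 15.0.

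A reader might infer that the SAP says follow-up differed. It raises a possible bias and reports no difference. SAP 3.3.6 describes a pause in enrolment at two sites, not in follow-up, and 7.5.3 allows the ETP to be done by phone. The pause therefore does not show worse retention in the IF period.

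A reader might also take the 39% rejection rate as evidence of a likely false IF benefit. It needs better follow-up in the IF period, which no section states. In the direction the SAP names, rejections favouring IF fall below 5%.

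Finally, the loss gaps are assumed, and Protocol 12.10 cites very low missing rates in the team's earlier work. Engagement is not co-primary (Protocol 2.1) and is treated as secondary (Protocol 12.11, SAP 9.0). Almost no missing data are expected for the main implementation outcome. These points limit the priority of the concern but do not close the gap.

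**Conclusion.** The point holds in a limited form. The plan reports missingness by period and equalises the contact window, but no inferential analysis shows how differential loss affects the period estimate. The complete-case method is planned for a different contrast.

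The size rests wholly on assumptions, because the documents give no loss rates. It is about 2 points per 5-point difference in loss if 40% of the lost were engaged, 1.25 if 25%, and zero if none. The documented direction is towards hiding an IF benefit. Neither an actual difference in follow-up nor a spurious benefit is supported by the documents. This is a cheap improvement to a secondary outcome and does not affect the main implementation result.

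**What to change.** Keep missing = failure as the primary rule. Add to SAP 7.5.2 and Table 24, using the final site-plus-period model and keeping known deaths as not engaged (Table 5 lists deceased among reasons for non-completion):

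- (a) a complete-case run of the period effect;
- (b) either multiple imputation by site and period using baseline variables and index-visit buprenorphine receipt, or a tipping-point grid that varies engagement among the lost separately by period;
- (c) a run that counts facility-confirmed engagement (ETF) when the ETP is missing.

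Report whether the direction of the effectiveness result holds across these runs. The Revised SAP already discusses results, so runs added after that point should be labelled post hoc. The cost is SAP wording, a few table rows and a few runs on data already held. The downside is that the conclusion may become more cautious.

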7.5.4 Secondary Analyses Related to the Primary Effectiveness Outcome

A secondary analysis akin to the primary effectiveness outcome will also be implemented that addressed potential surveillance bias. Sites continued to attempt contact with patient participants who did not attend the follow-up visit within the targeted window (44 days, inclusive). Due to the stepped wedge this may result in a bias in that patient participants enrolled earlier have more of a chance of obtaining the primary effectiveness outcome. An analysis will be performed for treatment engagement that requires the self-report to have been obtained within the 44-day target window. Other than this requirement the operational definition follows Section 7.3.

An additional secondary analysis of the treatment engagement outcome measure will be implemented to assess whether there are differences in the rate of engagement at Day 30 between those who received ED-initiated BUP and those who did not.

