10.2.8 Timeline Follow-back (TLFB)

The Timeline Follow-back procedure (Sobell & Sobell, 1992²⁸; Fals-Stewart, 2000³⁴) will be used to elicit the patient participant's self-reported use, quantity, and route of administration of opioids, marijuana, stimulants, benzodiazepines and alcohol. At enrollment, substance use is reported by the patient participant for the 7-day period prior to informed consent.²⁸ At the 30 day follow-up visit, substance use is reported for the 7 days prior to study day 30.

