3.3.2 Follow-up Visit

The Follow-up visit date is defined as the 30th day estimated post-index ED Visit discharge. The actual visit can occur later, but information is only collected about events that occurred within 30 days of the index ED visit discharge date.

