7.6.2 Secondary Effectiveness Outcomes

1. Self-reported days of illicit opioid use (past seven-days) as measured by TLFB method at 30 days: The following substances collected on TLFB method will be considered illicit opioid use if there is no prescription: heroin, oxycodone, hydrocodone, fentanyl, morphine, hydromorphone, meperidine, methadone, buprenorphine, oxymorphone, pentazocine, and codeine.
2. Overdose events (past 30 days) captured by participant self-report in ODE: The outcome will be scored from question 1 “On how many days in the past 30 days do you think you overdosed on opioids (you used more opioids than you should have used and were more sedated, drugged, or high than you wanted to be)?”
3. HIV risk taking behaviors (past 30 days) as captured in HST.
4. Healthcare service utilization (past 30 days).
5. Rates of illicit opioid negative urines at 30 days as captured on urine drug screen (UDS): A UDS will be considered negative for opioids if all of the following substances are negative: opiates (2000ng), oxycodone, methadone, opiates (300ng), buprenorphine and fentanyl. If a participant tests positive on the UDS for any of these substances and self-reports on TLFB that they have a prescription for any opioid, then the use will be considered licit (i.e., not illicit).

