[figure not shown]

Table 5: Summary of Patient Participant Disposition by Evaluation Period

	Baseline Evaluation Period	IF Evaluation Period	Total
Number of patient participants enrolled	N		
Number of study completers ¹	N (XX.x%)		
Number who completed the Day 30 follow-up visit within the window ²	N (XX.x%)		
Number of non-completers	N (XX.x%)		
Reasons for non-completion			
Failed to return to clinic and unable to contact	N (XX.x%)		
Incarcerated	N (XX.x%)		
Deceased	N (XX.x%)		
Terminated due to practical problems (no childcare, transportation, other)	N (XX.x%)		
Moved from area	N (XX.x%)		
Terminated due to AE/SAE	N (XX.x%)		
Terminated for other reason	N (XX.x %)		
Significant psychiatric risk (suicidal, homicidal, psychotic)	N (XX.x %)		
Withdrew consent/assent	N (XX.x %)		
Terminated for administrative issues	N (XX.x %)		
Terminated due to pressure or advice from outsiders	N (XX.x %)		
Feels treatment no longer necessary, cured	N (XX.x %)		
Feels treatment no longer necessary, not working	N (XX.x %)		

¹ Patient participants are defined as study completers if the Day 30 follow-up visit is completed as noted on the STC.

² Between 30 and 44 days, inclusive, past enrollment.

Table 6: Summary of Patient Participant Disposition by Site					
	MA Johns Hopkins ED	GNY Mount Sinai ED	OV University of Cincinnati ED	PNW Harborview Medical Center ED	Total
Number of patient participants enrolled	N				
Number of study completers ¹	N (XX.x%)				
Number who completed the Day 30 follow-up visit within the window ²	N (XX.x%)				
Number of non-completers	N (XX.x%)				
Reasons for non-completion					
Failed to return to clinic and unable to contact	N (XX.x%)				
Incarcerated	N (XX.x%)				
Deceased	N (XX.x%)				
Terminated due to practical problems (no childcare, transportation, other)	N (XX.x%)				
Moved from area	N (XX.x%)				
Terminated due to AE/SAE	N (XX.x%)				
Terminated for other reason	N (XX.x %)				
Significant psychiatric risk (suicidal, homicidal, psychotic)	N (XX.x %)				
Withdrew consent/assent	N (XX.x %)				
Terminated for administrative issues	N (XX.x %)				
Terminated due to pressure or advice from outsiders	N (XX.x %)				
Feels treatment no longer necessary, cured	N (XX.x %)				
Feels treatment no longer necessary, not working	N (XX.x %)				

¹ Patient participants are defined as study completers if the Day 30 follow-up visit is completed as noted on the STC.

² Between 30 and 44 days, inclusive, past enrollment.

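### The 44-day-window analysis covers treatment engagement only, although the urine outcome labelled as 30-day is the one that cannot be anchored to Day 30 at a late visit

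*SAP*

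**What the plan says.** SAP 7.5.4 states: "Sites continued to attempt contact with patient participants who did not attend the follow-up visit within the targeted window (44 days, inclusive"). It raises the possibility of surveillance bias, in that "patient participants enrolled earlier have more of a chance of obtaining the primary effectiveness outcome", and gives one remedy: "An analysis will be performed for treatment engagement that requires the self-report to have been obtained within the 44-day target window". The window is defined in the footnotes to SAP Tables 5 and 6 as "Between 30 and 44 days, inclusive, past enrollment".

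SAP 7.6.2 lists the secondary effectiveness outcomes. Item 5 is "Rates of illicit opioid negative urines at 30 days as captured on urine drug screen (UDS"). It has no collection-date rule. A positive screen counts as licit if the patient reports an opioid prescription on the timeline follow-back (TLFB). Protocol 10.2.8 fixes the follow-up TLFB by saying that "substance use is reported for the 7 days prior to study day 30".

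For reported events, SAP 3.3.2 says: "The actual visit can occur later, but information is only collected about events that occurred within 30 days" of discharge from the index ED visit. SAP 3.3.5 sets the follow-up window for overdoses, suicidal ideation, and ED visits and hospitalizations as baseline to Study Day 30.

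**The concern.** Engagement and TLFB use are both asked about a fixed date, so a patient seen on day 70 can still report on Day 30. A urine specimen has no such anchor. It shows recent use at the visit, whenever that is. The window analysis therefore protects an outcome that already refers to Day 30 and leaves out the one that cannot.

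Two things follow. A late specimen may be analysed as a 30-day result when it is not one. If late specimens are commoner in one evaluation period, part of the period difference in negative urines could then reflect when patients were tested and not the facilitation. Scoring can also mix dates, because a late positive is classified with prescription answers from the week before Day 30.

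**Working it through.** **1. The window.** The footnotes to SAP Tables 7 and 8 give a target of 30 days plus 14 days: 30 + 14 = 44. This reproduces the stated limit.

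**2. What each measure refers to at a visit on day v > 44.**
- Engagement: the Day-30 target date (Protocol 10.2.15).
- Days of illicit opioid use: the 7 days before Study Day 30 (Protocol 10.2.8).
- Overdose, ED visits and hospitalizations: baseline to Study Day 30 (SAP 3.3.5).
- Other reported events: within 30 days of index discharge (SAP 3.3.2).
- Urine: day v. The gap between the TLFB prescription information and the specimen is v − 30 days, which is 14 at day 44 and 40 at day 70.

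**3. Opportunity for a late visit, by period.** Inputs are the enrollment start and end dates in SAP 3.3.6. Opportunity = assumed last contact date − enrollment date. The documents give no last contact date, so three assumptions were tried. The first two, in days:

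| Site | Stop 44 days after the site's own IF period ends: baseline / IF enrollees | Stop 44 days after the last site closes (10/4/2020): baseline / IF enrollees |
|---|---|---|
| Johns Hopkins | 591–955 / 44–408 | 953–1,317 / 406–770 |
| Mount Sinai | 593–957 / 44–410 | 866–1,230 / 317–683 |
| Cincinnati | 681–1,045 / 44–499 | 771–1,135 / 134–589 |
| Harborview | 686–1,050 / 44–504 | 686–1,050 / 44–504 |
| Mean of site midpoints | 820 / 250 | 1,001 / 431 |

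The midpoints assume even enrollment within each period and ignore the COVID-19 pause. The difference in means is about 570 days either way (820 − 250; 1,001 − 431). At every site the shortest baseline opportunity exceeds the longest IF opportunity, for example 591 − 408 = 183 days. That margin is the gap between the two enrollment periods, so it holds for any single stop date at a site.

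The third assumption is that attempts for each period stopped 44 days after that period closed. Baseline opportunity is then 44 to 408 days at every site (364 + 44), against IF maxima of 408, 410, 499 and 504. The baseline excess disappears. SAP 7.5.4's own remark about earlier enrollees fits the first two assumptions better than the third.

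**4. Possible size for urine.** Shift in the period difference = (late share in baseline − late share in IF) × (difference in negative rate, late against on-time). Every input is assumed:
- 10% v 5% late, 10-point rate difference: 0.05 × 0.10 = 0.5 points
- 20% v 10%, 10 to 20 points: 0.10 × 0.10 to 0.20 = 1 to 2 points
- 30% v 10%, 10 to 20 points: 0.20 × 0.10 to 0.20 = 2 to 4 points

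If late specimens are less often negative, the IF benefit is overstated. If they are more often negative, it is understated.

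**The case against.** The strongest reply is that no harm has been shown. The documents contain no late-visit counts, and SAP 7.5.4 speaks only of what may happen to the engagement outcome. A reader might infer that late visits are known to concentrate in the baseline period, or that visits could occur without limit. Neither is stated. The dates show greater opportunity under a single stop date, and the limit is unstated, not absent. Telephone visits yield no urine (Protocol 9.4), so some late contacts add nothing to this outcome. It is a secondary outcome, and SAP 9.0 treats secondary findings as hypothesis-generating. All of this stands and limits the weight of the point.

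A second tempting inference is that the overdose, HIV-risk and utilization items also slide with the visit date, because they ask about the past 30 days. The overdose question, for instance, reads "On how many days in the past 30 days do you think you overdosed on opioids". The documents do not support that. SAP 3.3.2 limits collected events to 30 days from index discharge, and SAP 3.3.5 fixes overdoses and ED visits and hospitalizations at baseline to Study Day 30. What remains is that the printed overdose item carries no anchor and the HIV-risk item has none of its own. The ideation item in SAP Table 36 asks about two weeks although 3.3.5 gives a longer window. These are wording differences to reconcile, not evidence of mistimed data.

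None of this answers the urine point: no recall instruction can move a specimen to Day 30.

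**Conclusion.** The point holds for the urine outcome only. The SAP identifies a timing problem, restricts one outcome to the window, and leaves the outcome most exposed to timing without a collection-date rule or a window analysis.

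That timing could differ by period rests on each site having one stop date for contact attempts. The Revised SAP's statement that the two periods hardly overlapped supports equating early with baseline enrollees. The range of about 0.5 to 4 points is illustrative; actual size and direction cannot be derived from the documents. The change is an inexpensive safeguard for one secondary comparison and does not bear on the primary implementation result.

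The documents do not support making Days 30 to 44 the main rule for every secondary effectiveness outcome. That would discard late reports that the SAP ties to the intended period, and would replace a possible timing bias with selection on prompt attendance.

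**What to change.** - In SAP 7.5.4, extend the 44-day analysis to item 5 of 7.6.2: use urines collected on Study Days 30 to 44 and show the result beside the all-visits result. Apply the window to the specimen date and leave later specimens out of the restricted analysis.
- Report the distribution of days from enrollment to specimen by evaluation period. If late specimens are few or balanced, that settles the matter.
- In SAP 7.6.2, reconcile the past-30-days wording of the overdose, HIV-risk and utilization items with the Day-30 anchor in 3.3.2 and 3.3.5, and confirm how the questions were asked. Keep the late reports.

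The cost is SAP wording and one further run of an existing model. Within-window completion is already tabulated in Tables 5 and 6, so visit timing is available. The downside is fewer urines, and so less precision, in the restricted analysis.

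### The 44-day engagement analysis limits when the self-report is obtained but not when the facility confirms it, so a difference in confirmation between periods is not ruled out

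*SAP*

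**What the plan says.** SAP 7.3 builds the engagement outcome from two forms. For the first, "The outcome will be based on patient participant self-report on the Engagement in Treatment: Participant (ETP) form"; that report must then be "confirmed by facility and/or treating clinician on the Engagement in Treatment: Facility (ETF) form". Where a patient reports treatment "but there is no confirmation from a facility or clinician", the patient is scored as not engaged. An ETF whose engagement item is blank makes the outcome missing, and SAP 7.5.3 scores missing outcomes as failures. A self-report of no treatment is a failure whatever the ETF shows, and an ETF without a self-report is missing, hence also a failure.

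SAP 7.5.4 notes that sites went on trying to reach patients who missed the follow-up window, and that because of the stepped design "patient participants enrolled earlier have more of a chance of obtaining the primary effectiveness outcome". Its remedy is: "An analysis will be performed for treatment engagement that requires the self-report to have been obtained within the 44-day target window". It then adds: "Other than this requirement the operational definition follows Section 7.3".

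No deadline for the ETF appears in SAP 7.3 or 7.5.4, or in the protocol's accounts of confirmation (9.3, 10.2.15 and 14.8.1). Protocol 14.8.1 places verification after the patient's report.

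**The concern.** The 44-day analysis exists to show whether unequal time for ascertainment affects the engagement result. Success has two required components, and the analysis equalises the time allowed for only one. A patient who reports treatment on Day 35 and has no ETF is a failure until a confirming ETF arrives, and it may arrive at any later date. At each site the baseline patients came first, so the SAP's own reasoning about enrolment order could also apply to confirmation.

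At stake is how much reassurance the analysis gives. If it agrees with the main engagement result, a reader may conclude that ascertainment was equal between periods, when only the timing of the self-report was made equal. The model in the Revised SAP section would not correct this: it removes calendar time and keeps only site and evaluation period.

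**Working it through.** **1. The window.** The footnote to SAP Table 7 gives a 30-day target plus 14 days: 30 + 14 = 44. This matches SAP 7.5.4.

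**2. Scoring under the 44-day rule** (SAP 7.3, 7.5.3 and 7.5.4 together):

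| Self-report by Day 44 | ETF | Scored as |
|---|---|---|
| In treatment | Confirms, at any date | Success |
| In treatment | None, or none that confirms | Failure |
| In treatment | Present, engagement item blank | Missing, so failure |
| Not in treatment | Anything | Failure |
| None by Day 44 | Anything | Failure |

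The last row shows that a late self-report can no longer produce a success. The first two rows show that, among timely reporters of treatment, the outcome still depends on an undated event.

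**3. Time available for confirmation.** Enrolment dates are in SAP 3.3.6. The documents do not say when facility contact stopped. Assume it stopped at each site 44 days after that site's last enrolment. For a patient enrolled midway through each period, the days available beyond Day 44 are:

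| Site (order of start) | Baseline | IF | Difference |
|---|---|---|---|
| First | 729 | 182 | 547 |
| Second | 731 | 183 | 548 |
| Third | 819 | 227.5 | 591.5 |
| Fourth | 824 | 230 | 594 |

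The difference column does not depend on the assumed stopping date, provided each site has one stopping date for both periods. It measures opportunity only. It does not show that confirmation differed.

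**4. Effect on the risk difference.** Let *q* be the share self-reporting treatment by Day 44, taken as equal in both periods, and *c* the probability that confirmation is ever obtained. Then

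residual bias = *q* × (*c*_IF − *c*_baseline).

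Neither *q* nor *c* is in the documents. Protocol 12.5 anticipates 25% engagement at baseline and 40-50% under IF. These values stand in for *q* below, and the gaps are assumed:

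| *q* | Gap 0 | Gap 3 points | Gap 5 points | Gap 10 points |
|---|---|---|---|---|
| 0.25 | 0 | -0.75 | -1.25 | -2.5 |
| 0.40 | 0 | -1.2 | -2.0 | -4.0 |
| 0.50 | 0 | -1.5 | -2.5 | -5.0 |

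For example, 0.25 × (-0.03) = -0.0075 and 0.25 × (-0.10) = -0.025. Entries are percentage points, IF minus baseline, for gaps favouring baseline. A gap favouring IF gives the same sizes with a positive sign. The hypothesised effect is 40 − 25 = 15 to 50 − 25 = 25 points.

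**5. Time left for the last enrollee.** Enrolment ended on 4 October 2020, so the last possible Day 44 is 17 November 2020. SAP version 1.0 was approved on 14 June 2021, 209 days later. No database lock date is given.

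**The case against.** Several stronger readings are tempting, and the documents do not support them.

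- *That the bias named in SAP 7.5.4 survives.* It does not. The SAP names late contact with patients, and a self-report after Day 44 can no longer yield a success. What may remain is a separate route through facilities.
- *That the ETF decides success.* It is one of two necessary components and can never create a success alone.
- *That facilities were chased unequally.* SAP 7.5.4 describes continued contact with patients, not facilities. Verification follows the report and may usually have been prompt.
- *That a late enrollee could not be confirmed.* With no lock date, and 209 days between the last possible Day 44 and approval of SAP version 1.0, this cannot be said.
- *That any residual bias favours baseline and masks an IF effect.* Protocol 11.9 has IF establishing links with community treatment providers, while baseline referral follows existing practice. Closer links could raise confirmation in the IF period and reverse the sign. If baseline is favoured, the bias works against the one-sided IF hypothesis and could not produce a false positive.
- *That the bias is several points.* For instance, 45% self-reporting with 95% against 85% confirmation gives 0.45 × (-0.10) = -4.5 points. But it implies baseline engagement of 0.45 × 0.95 = 42.8%, well above the protocol's 25%, and the 10-point gap has no source.

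This is also a secondary analysis of an outcome that protocol 12.11 itself treats as secondary, so the main implementation test is untouched. All of these objections stand as limits on the point. None supplies the missing time limit on confirmation.

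**Conclusion.** The point holds in a limited form. The 44-day analysis does what it says about late self-reports, but it leaves facility or clinician confirmation without a time limit. A possible ascertainment difference between periods is therefore not ruled out. Its size and direction are unknown and it could be zero. With 25% self-reporting treatment by Day 44, and confirmation gaps of 3 to 10 points favouring baseline, the bias would be -0.75 to -2.5 points, small against the hypothesised 15 to 25. That range rests wholly on the assumed share and gaps. The matter justifies an inexpensive tightening of one secondary analysis. It does not show that the engagement result is biased.

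**What to change.** First check that the ETF or the Facility Contact Log records the dates needed; the SAP lists these forms by name but does not show their fields. Then, in SAP 7.5.4 and for this secondary analysis only:

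1. Keep the self-report condition, and also require the ETF within one fixed limit after the Day-30 target date, the same in both periods. Make it no longer than the time the last enrollee had before database lock.
2. Score a later ETF as not confirmed.
3. Tabulate days from Day 30 to ETF by period and site, so that a reader can see whether any gap exists.
4. Report the result beside Table 24. SAP 15.0 lists no table for the 44-day analysis.

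The Revised SAP section already reports engagement findings, so the analysis should be labelled as added afterwards. The limit should be set from calendar dates, not from outcomes.

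The cost is one sentence, one date filter and one small table, if the dates exist. The downside is that some true but slowly confirmed engagements are lost in both periods.
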